eligibility criteria. Because the medication experiment feature is not clinically relevant for adolescents taking a non-stimulant ADHD medication, and this is a key portion of the intervention, those who are taking non-stimulant medications will not be included. At the time of enrollment, families will schedule an in-person visit during which parents and adolescents will complete baseline measures and receive training on how to use mehealth for ADHD. If families are unable to complete this visit in-person, consent and assent will be completed over the phone, measures will be sent electronically via REDCap, and study staff will conduct training on how to use mehealth for ADHD remotely (i.e. using Zoom to share screen). Before participants are randomized, we will verify the number of days covered with medicine based on dispensing data. This estimate will be used for the stratified randomization procedure. Participants will be randomized into either the intervention group or control group. The control group will continue to use the standard mehealth for ADHD software, and the intervention group will receive access to the intervention features. Because medication use varies widely during the summer months and school holidays, the intervention will begin just prior to the start of the school year to reduce variation in medication continuity based on time of year. The trial will end 4 months later. At that time, families will complete end of study measures, and pharmacy dispensing records will be obtained. The end of study measures may be completed in-person or electronically.

DURATION:

This IRB protocol covers the second phase of the study during which we will test the medication continuity tools developed in collaboration with our stakeholders during the first phase of the study. Families will be enrolled in the study for approximately 10 months.

PROCEDURES:

Research Participant Recruitment and Obtaining Informed Consent

All participants will be recruited from Cincinnati Children’s Hospital PPCC. A research assistant will initiate phone contact with PPCC patients who appear eligible based on their age,

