being registered on mehealth for ADHD, and having less than 80% of days covered with ADHD medicine based on prescriptions written in the past year. Phone calls will serve to provide information about the study and answer questions. Those who express interest will complete screening questions needed to verify eligibility criteria. If they are eligible, the research assistant will schedule an in-person visit during which they will review the full consent and assent form with the parent and adolescent. After we review the content of the consent form with the parent, they will record their consent on REDCap using a study-specific consent form modeled after the eConsent demo on the REDCap Resource Center. We will also explain the study to children (in language appropriate to them; see below), and record their assent in REDCap. Following this, participants will complete their baseline surveys and receive a ClinCard to reimburse them for their study visit. If families are unable to complete this visit in-person, it will be completed remotely via phone call and/or video conferencing.

Inclusion/Exclusion Criteria

Inclusion Criteria: Participants for the study must meet all of the following criteria:

- a. Consent: The family must provide informed consent by parents or legal guardians
- b. Assent: Children must provide assent to participate in the study
- c. Ages 11-15
- d. Treated for ADHD by pediatrician
- e. First prescribed ADHD medicine more than one year prior to enrollment
- f. Have < 80% of days covered by ADHD medicine in the past year of treatment (based on pharmacy dispensing records)
- g. Filled at least one prescription for a stimulant medication in the past year

Exclusion Criteria: Participants will be excluded from the study if they meet any of the following criteria:

- a. Poor understanding level: The participant and parent cannot understand or follow instructions given in the study.
- b. Have \geq 80% of days covered by ADHD medicine in the past year of treatment (based on pharmacy dispensing records)
- c. Do not have reliable access to the internet at their home or another location.
- d. Will not permit their child to access the internet for study related activities
- e. Are not able or willing to send or receive text messages

Intervention

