Overview: Pediatricians can play a critical role supporting medication management and continuity of treatment, if they have the right information and teens and parents are actively engaged in the process. When teen and parent responses to the assessment battery suggest that the teen may benefit from additional titration or a trial on/off medication, the teen and parent will all be alerted to the recommendation. Adolescents and parents will be guided through a series of customized steps using program routines, called wizards. A software wizard is a user interface type that presents a sequence of dialog boxes that lead the user through a series of steps towards goal completion. Wizards will prompt patients and parents to identify, prioritize, and discuss behavioral targets to monitor during titration or trial on/off medicine.

Medication titration: Dosage adjustment and/or titration of a medicine with a different chemical ingredient will be recommended to optimize effectiveness when a teen/parent indicate they are interested in trying a new medication or dose. Parents and adolescents who express interest in changing medicine or dose will be directed to make an appointment with their pediatrician to discuss what the best option is for the family. Videos that describe different medication/treatment options will also be available for the parents and adolescents.

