Pediatrician supervised trial on/off optimal dosage: A structured trial on/off medicine will be recommended when teen/parent responses to the assessment battery indicate uncertainty about whether medicine is still needed because the teen appears to be thriving. The intervention delivers training on how to conduct a high quality trial on/off medicine will include the ADHD clinical practice guideline recommendations (Pliszka 2007; AAP 2011) that differentiate these trials from the common clinical practice of stopping medication during summer or holiday breaks from school (e.g., best when there are few transitions or demands [mid school year], avoid at beginning of any school year, especially at the start of junior/senior high school, discontinue medication for 2-4 weeks, monitor target outcomes). The trial on/off medicine is designed to reduce ambivalence about medicine (i.e. document improvement among teens that still benefit) which may motivate self-directed changes to support medication continuity. Of note, trials on/off non-stimulant medication have limited utility given that atomoxetine and guanfacine take 4-6 weeks before maximal response is achieved and guanfacine can't be abruptly stopped due to risk of rebound hypertension (Froehlich et al. 2013). Accordingly, pediatricians will advise each family regarding the value of conducting an on/off trial in each situation.

Symptom & side effect monitoring: The mehealth for ADHD intervention enables the tracking of ADHD symptoms, medicine side effects, and other outcomes that are important to

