12. Implementation factors of UTBC influencing medication continuity (Appendix K & L): These factors will be measured using the Adolescent and Parent Medication Barriers Scales (AMBS and PMBS) (Simons et al. 2007; Simons et al. 2010). Adolescents and parents respond using a 5-point Likert-like scale from “strongly disagree” to “strongly agree” to report perceived barriers to medication taking. Both the adolescent scale (17-items) and parent scale (16-items) have strong internal consistency for total score and the four factor-analytically derived subscales: ‘Disease frustration/adolescent issues’, ‘Regimen adaptation/cognitive’, ‘Ingestion issues’, and ‘Parent reminder’. For criterion-related validity, adolescents classified as non-adherent had significantly higher barrier scores than those classified as adherent. In prospective validation studies, the adolescent-perceived barriers of ‘Disease frustration/adolescent issues’ and parent-perceived barriers of ‘Regimen adaptation/cognitive issues’ were associated with poorer adherence to medication taking (Simons et al. 2010).
13. Medication Continuity: We will calculate the percentage of days covered with medicine based pharmacy dispensing records and verified by parent report of ADHD service use using the reliable Services for Children & Adolescents – Parent Interview (Eaton Hoagwood et al. 2004). This measures ADHD service use, including office visits and medication use. We have successfully obtained pharmacy dispensing records via parental permission for 95% (155/164) of subjects across 2 studies (R01 MH074770, K23 MH083027) ([name] et al. 2013; [name] et al. 2016). Pharmacy dispensing records provide an objective, unobtrusive, reliable measure that is a well-accepted proxy for medication consumption (Steiner et al. 1997) that was significantly correlated with the more expensive and invasive Medication Event Monitoring System (MEMSCap™) which uses a microprocessor in the medication container cap to record the day and time of each vial opening (Farley et al. 2003).
14. Medication Diversion: Self-report of giving away, trading, or selling ADHD medicine to someone for whom it was not prescribed will be collected via a confidential web-based survey used in past population-based studies of middle/high school students. (Boyd et al. 2007; McCabe et al. 2011a).

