### **2.2.4 Missing data**

We will use pharmacy dispensing records to calculate our primary outcome for all study participants unless consent is withdrawn.

For secondary outcomes, missing outcome data could occur for several reasons such as item nonresponse, lost to follow-up, and data collection errors. The average score of the total number of available items within a factor score will be used to account for missing outcome data.

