#### 2.3.2 Primary outcome analysis

*Primary outcome:* Medication continuity as measured by proportion of days covered with medicine during the 4-month trial.

- Number of days covered with medicine is calculated from audit of prescriptions dispensed.

For the primary outcome, the dependent variable will be a proportion of the number of days covered with ADHD medicine during the 4-month trial. Differences between intervention and control groups on this outcome will be evaluated using a two-sample t-test or Wilcoxon rank sum test.

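### Does the lack of a written rule for overlapping fills leave the primary outcome, days covered, in need of a change?

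*SAP*

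**What the plan says.** SAP 2.3.2 makes the primary outcome the proportion of days covered during the 4-month trial and gives the source of the count: "Number of days covered with medicine is calculated from audit of prescriptions dispensed". SAP 2.2.4 adds: "We will use pharmacy dispensing records to calculate our primary outcome for all study participants unless consent is withdrawn". The protocol (Outcome measures, item 13) says: "We will calculate the percentage of days covered with medicine based pharmacy dispensing records and verified by parent report of ADHD service use". Of the parent interview it says: "This measures ADHD service use, including office visits and medication use".

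Two intervention components bear on dispensing. Under Medication titration, for teens or parents interested in a new medicine or dose: "Dosage adjustment and/or titration of a medicine with a different chemical ingredient will be recommended to optimize effectiveness". Under the supervised on/off trial, the guidance passed to families includes: "discontinue medication for 2-4 weeks, monitor target outcomes". The protocol's Study Design section limits the new tools to one arm: "The control group will continue to use the standard mehealth for ADHD software, and the intervention group will receive access to the intervention features".

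The same kind of count is used before the trial starts. The entry limit, under "80% of days covered by ADHD medicine in the past year of treatment (based on pharmacy dispensing records", comes from dispensing data, and both documents use past-year days covered to stratify the randomisation.

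**The concern.** Turning a list of fills into covered days needs a rule for overlap. If a teen changes medicine on day 10 of a 30-day fill, about 20 days of the replaced medicine remain. A count that carries overlap forward turns those days into later covered days. A count that takes each fill from its own date does not. Both are consistent with the SAP, so one record can have two scores.

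This matters more than usual here because the recommendation to change dose or medicine reaches only the intervention arm. If changes are commoner there, carry-forward could credit the intervention with coverage that did not occur. The SAP is dated 12/15/2021 and gives a study end date of 5/24/21, so an unwritten rule could be chosen with the outcomes in hand. The on/off trial and the protocol's mention of parent report looked like two further places where the score might be open.

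**Working it through.** **1. The plan's own figure.** Inputs from the protocol's Power and Sample Size section: difference 66.2 − 50.5 = 15.7, SD 16.5, two-sided 0.05, power 80%. n per group = 2 × [16.5 × (1.960 + 0.842) / 15.7]² = 17.34, rounded up to 18, as stated. The standard error of the difference is 16.5 × √(2/18) = 5.5 points. The overlap question does not touch this.

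**2. One record, two rules.** Assumptions not given in the documents: a 120-day window and 30-day fills. Take fills on days 1, 11 (the change), 56 and 101.
- No carry-forward: days 1–40, 56–85 and 101–120, so 40 + 30 + 20 = 90, and 90/120 = 75.0%.
- Carry-forward: the second fill runs over days 31–60 and the third over days 61–90, so 90 + 20 = 110, and 110/120 = 91.7%.

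The gap is 16.7 points, but this example is well above the average.

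**3. Average over cases.** Let fills come every T days, so usual coverage is 30/T. Put one change on each of the 120 calendar days and on each of days 1–29 after a fill, when supply remains: 120 × 29 = 3,480 cases for each T. Changes on days 30 to T − 1 leave no supply and create no overlap, so the average over the whole cycle is the supply-remaining figure × 29/(T − 1).

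| T | Usual coverage | No carry | Carry | Gap, supply remaining | Gap, any day in the cycle |
|---|---|---|---|---|---|
| 30 | 100% | 100% | 100% | 0 | 0 |
| 38 | 78.9% | 81.5% | 87.6% | 6.07 | 6.07 × 29/37 = 4.8 |
| 45 | 66.7% | 71.0% | 78.7% | 7.65 | 7.65 × 29/44 = 5.0 |
| 59 | 50.8% | 56.9% | 65.3% | 8.40 | 8.40 × 29/58 = 4.2 |

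The last column suits this population better. Teens enter because their supply has gaps, and a change made during a gap leaves nothing to carry.

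**4. Arm level.** Let u be the excess share of intervention teens with one change over control. The shift between rules is u × gap, with gaps from 4.2 (any day) to 8.4 (supply remaining). If the whole shift is treated as error, with no true difference, the two-sided rejection rate is Φ(−1.96 + shift/5.5) + Φ(−1.96 − shift/5.5).

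| u | Shift (points) | Rejection rate (nominal 5%) |
|---|---|---|
| 10% | 0.4–0.8 | 5.1–5.3% |
| 25% | 1.1–2.1 | 5.4–6.7% |
| 50% | 2.1–4.2 | 6.7–11.9% |
| 100% | 4.2–8.4 | 11.9–33.3% |

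The documents give no value for u. These rates are upper readings, because replaced supply is sometimes still used and carry-forward is then partly right.

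**5. The on/off trial.** An off period creates no overlapping supply. With fills on days 0, 30 and 88 around a 28-day gap, both overlap rules give 75.0%. With refills kept on schedule, dispensing shows no loss. Scores of 97.8% (off days removed from the denominator) or 98.3% (off days counted as covered) need a rule that the SAP does not contain: its denominator is the 4-month trial and its source is dispensing. Lower coverage from refills not collected is part of the package's effect. The protocol also advises against on/off trials at the start of a school year, while the 4 months begin just before one.

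**6. The source.** Item 13 of the protocol's outcome measures and SAP 2.2.4 and 2.3.2 all take the value from dispensing. Parent report is a check in the protocol and is not named as a source in the SAP. No passage lets it override the records.

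**7. When the method was needed.** Study Design requires days covered to be verified from dispensing before randomisation, for stratification, and the entry criteria need it too. A way of counting therefore had to exist before any outcome was seen.

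**The case for a change.** The strongest case for a change is that the primary outcome should not depend on an unwritten choice, least of all when the triggering event is encouraged in one arm and the SAP postdates the end of the study. With 18 per group, two affected teens are already more than 10% of an arm, and a single record can move by 16.7 points. Writing the rule down would cost a paragraph.

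Much of this is fair. The documents contain no overlap rule, the arithmetic is right, and the pre-randomisation method is inferred because it is not described. At very high uptake the shift would not be small.

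Three things limit it. First, the imbalance is assumed. The portal directs interested families to book an appointment; control families can change dose in usual care; and the protocol's remark that experiments are unlikely in control does not cover dose changes. Second, the obvious remedy, excluding replaced supply, is itself debatable, since it under-counts when the old supply is still used. Applied to the outcome alone, it could also break consistency with the past-year figure used for entry, stratification and the protocol's change score under Hypothesis 4. Third, the date carries limited weight: the SAP is labelled version 1.1, so its date need not be that of its first version, and the counting method was needed before randomisation.

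**Conclusion.** No change to the plan follows. This is missing detail that analysts fill sensibly. The SAP states no rule that gives a wrong answer, and a standard days-covered count, carried over from the baseline calculation and applied alike in both arms, supports a sound comparison. The choice of overlap rule is worth about 4 to 5 points for a teen with one change at any time, or 6 to 8 if supply remains: about 0.4 to 0.8 points on an arm mean per 10% of teens, against 15.7 planned. The on/off trial and the parent-report check do not add to it.

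The conclusion rests on an assumed 120-day window, 30-day fills, at most one change per teen, and an excess of changes in the intervention arm that is not extreme. The documents do not give that last figure. Naming the overlap rule when results are reported would help readers, but that is a matter of reporting.

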15. Client Satisfaction Questionnaire (CSQ) (Attkisson et al. 1982) is an 8-item unidimensional measure of client satisfaction with services. Psychometric properties, operating characteristics, and coefficient alpha (.93) are very strong for this measure which we will collect from adolescents and parents.
16. Decision Making Involvement Scale (DMIS) (Miller et al., 2012): is a 30-item scale to measure adolescent involvement in a decision. The five subscales are: “Child Seek” (child asks for an opinion or information from parent), “Child Express” (child expresses an opinion or information to parent), “Parent Seek” (parent expresses advice or opinion to child), “Parent Express” (parent expresses advice or opinion to child), and

“Joint/Options” (negotiation or brainstorming between parent and child). We will collect this measure from adolescents and parents.

DATA ANALYSIS

Hypothesis testing:

Each hypothesis examines part of the mechanism underpinning intervention impact on medication continuity.

Hypothesis #1: *Adolescents will use greater than 80% of relevant intervention components.* For each subject in the intervention group, we will calculate the proportion of **recommended** intervention components that were utilized by the subject during the study. The mean and 95% confidence interval (CI) will be computed to give a range estimate of the fidelity measure. To evaluate our hypothesis, we will utilize the computed CI to determine if 80% or greater is a plausible value, such that if the CI includes a value of 80% or greater we will reject the null hypothesis. We will also examine the temporal distribution of use for each of the recommended components.

Hypothesis #2: *Use of the intervention components will be related to improvements in the targeted UTBC factors.* Using a generalized linear model, we will test whether the intervention addressed the UTBC factors (i.e., pre-intention factor scales and ABMS/PBMS total and subscale scores). Model predictors will include a fixed effect indicator of time point (baseline or end of study). A significant effect of time point in the expected direction would indicate UTBC factor improvement.

Hypothesis #3: *Medication continuity will be higher in the intervention group compared to the control group.* We will compare the percentage of days covered with medicine using a two-sample t-test.

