Hypothesis #4: *Pre-post changes in UTBC factors will be related to increases in medication continuity.* We will calculate the change score for each relevant UTBC factor (end of study minus baseline) and the change score for medication continuity (percentage of days covered at end of study minus percentage of days covered in the 12 months prior to study). We will model the association between change in UTBC factor scores (independent variable) with change in medication continuity (dependent variable) using generalized linear mixed model. A significant effect of change in UTBC factor scores (beta coefficient) in the expected direction would indicate changes in UTBC factor scores were associated with medication continuity improvement.

Exploratory analyses:

We will conduct descriptive analyses to characterize rates of diversion at baseline and at the end of study using a McNemar's test to see if rates differ. We will summarize responses to the client satisfaction questionnaire descriptively as this may facilitate future dissemination.

Power and Sample Size:

The study would require a sample size of 18 for each group (i.e. a total sample size of 36), to achieve a power of 80% and a level of significance of .05 (two sided), to detect a difference in means between the intervention and the control groups of 15.7% (i.e. 66.2% vs. 50.5%) on the percentage of days covered with medicine assuming a pooled standard deviation of 16.5. Due to the low intra-class correlations observed in previous studies of ADHD medication continuity (ICC = 0; [name] et al. 2018), the analyses will not account for the nesting of patients within physicians. We will recruit 44 patients to ensure that 36 are retained at the end of the study. A retention rate of 80% (36/44) is conservative in light of the 12-month retention rate of 92% achieved by [name] in his current trial. We will use a stratified blocked randomization procedure to ensure baseline medication continuity is evenly distributed in both arms.

Scientific Rigor:

The RCT is a rigorous design to test efficacy of our intervention. We will explicitly address whether the intervention engages the mechanism underlying medication continuity and therefore warrants further testing in a future larger trial. Our preliminary data strongly supports the importance of the problem, intervention targets identified, and the feasibility of the approach in our hands.

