Official Title of the study: **Randomized Controlled Trial of Web Based Tools to Improve Medication Continuity in Adolescents With ADHD**

NCT number: **NCT04386096**

Document name: **Statistical Analysis Plan**

Date of the document: **12/15/2021**

The results of the Web Based Tools study will be assessed as described in this document. This statistical analysis plan begins with an overview of the key components of the study, including its design, objectives, and outcomes measures. This is followed by a detailed description of the statistical analyses that will be utilized to address study hypotheses.

**1. Overview of study:** This study used a parallel group randomized control trial to test whether an intervention engages the proposed mechanism underlying medication continuity and improves outcomes. Adolescents and their parents that agreed to participate in the study were randomized to receive either the intervention (MeHealth for ADHD software with medication continuity tools) or the control group (MeHealth for ADHD software with no medication continuity tools). We used a stratified randomization procedure to ensure that the intervention and control groups were balanced with respect to the number of days covered with ADHD stimulant medication in the past year based on dispensing data. We planned to enroll a total of 44 adolescents aged 11-15 with ADHD with poor medication continuity from Cincinnati Children's Pediatric Primary Care Clinic (PPCC) in order to retain  $\geq 36$  subjects needed based on our sample size calculation.

**1.1 Study Objective:** Test a multi-component intervention that systematically identifies and targets aspects of the Unified Theory of Behavior Change (UTBC) model most relevant for each adolescent with poor ADHD medication continuity.

Working hypothesis 1: compared to the control group, the intervention group will have greater medication continuity as measured by number of days covered with medicine at the end of the study.

Working hypothesis 2: compared to the control group, the intervention group will have improved outcomes as measured by change in the Unified Theory of Behavior Change factors.

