### **1.4 Schedule of visits and time points of interest**

- Baseline survey (baseline, after consent, usually a few days after)
- Medication continuity over past year obtained at baseline
- End of study survey (4 months post study start date)
- Medication continuity at end of study (average of 4 months)

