### Demographics and Clinical Characteristics, Patient and Parent:

Demographic and clinical characteristics as measured at baseline will be summarized by trial arm.

Variables to be summarized are: parent age, parent race and ethnicity, parent sex, child sex, child age, child race and ethnicity. Variables will be summarized using descriptive statistics appropriate for each type of data item.

Baseline characteristics with large differences between groups will be included in analyses evaluating the effectiveness of the intervention.

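### The primary test leaves out the past-year days-covered value used to stratify randomisation; if that value is prognostic, the unadjusted test is conservative and its interval needlessly wide

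*SAP*

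**What the plan says.** Under Hypothesis #3 the protocol plans: "We will compare the percentage of days covered with medicine using a two-sample t-test". SAP 2.3.2 keeps this and adds a rank alternative: "Differences between intervention and control groups on this outcome will be evaluated using a two-sample t-test or Wilcoxon rank sum test". Neither version has a covariate.

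The baseline counterpart of the outcome is known before allocation. Protocol, Study Design, has days covered verified from dispensing data before randomisation and adds: "This estimate will be used for the stratified randomization procedure". Power and Sample Size says: "We will use a stratified blocked randomization procedure to ensure baseline medication continuity is evenly distributed in both arms". SAP section 1 confirms it: "We used a stratified randomization procedure to ensure that the intervention and control groups were balanced with respect to the number of days covered", meaning stimulant coverage over the past year. SAP 1.4 lists "Medication continuity over past year obtained at baseline". The only outcome analysis that uses this value is the protocol's Hypothesis #4 change score, which is not the primary comparison.

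The one provision for adjustment is in SAP 2.3.1: "Baseline characteristics with large differences between groups will be included in analyses evaluating the effectiveness of the intervention". It gives no threshold, and the variables listed with it are parent and child age, sex, race and ethnicity. Past-year coverage is not among them.

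On the number analysed, SAP 2.2.4 says: "We will use pharmacy dispensing records to calculate our primary outcome for all study participants unless consent is withdrawn". The primary analysis may therefore include closer to 44 adolescents than 36.

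**The concern.** Stratifying on a prognostic factor reduces the true sampling variance of the difference between arms. A two-sample t-test does not see this. Its standard error uses the full within-arm variance, including the part that stratification has already balanced out. The reported standard error is then too large, the test rejects less often than 5% under the null, and the interval is too wide. A model containing the baseline value corrects the standard error and also removes the baseline variation left within strata.

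The imbalance rule in SAP 2.3.1 does not fill the gap. It makes the model depend on the observed data. A factor balanced by design is among the least likely to trigger it. Neither test named in 2.3.2 can carry a covariate if it is triggered. With 36 to 44 adolescents and one primary comparison, the lost precision could matter, and the variable needed to recover it is already in the database.

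**Working it through.** **Inputs from the protocol (Power and Sample Size).** Difference 15.7 points (66.2% v 50.5%), SD 16.5, two-sided 5% level, 80% power, 18 per arm, 44 recruited to retain 36.

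**Assumptions.** The correlation r between past-year and 4-month coverage is not in the documents; 0 to 0.6 is used. Stratum cut-points and block size are not given either; a median split with 1:1 allocation within strata is used. The outcome is simulated as normal.

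**1. The plan's own figure.** n per arm = 2(1.96 + 0.8416)² × 16.5² / 15.7² = 17.34, rounded up to 18. This reproduces. Power at 18 per arm is 81.4% by the normal approximation and 79.2% by the noncentral t (86.9% at 22 per arm).

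**2. Closed form for the adjusted model.** Residual SD = 16.5 × √(1 − r²). The standard error is residual SD × √(2/18), with 36 − 3 = 33 degrees of freedom.
- Unadjusted: standard error 16.5 × √(2/18) = 5.5; 95% half-width 11.2 points.
- r = 0: power 79.1%, against 79.2% unadjusted; the cost is one degree of freedom.
- r = 0.3: residual SD 15.74, power 82.7%, half-width 10.7.
- r = 0.5: residual SD 14.29, power 89.2%, half-width 9.7.

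**3. Simulation of both analyses under stratified allocation, N = 36.** 40,000 runs per cell; the Monte Carlo standard error of a power near 80% is √(0.8 × 0.2 / 40,000) = 0.2 points.

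| r | Power, t-test | Power, adjusted | Type I error, t-test | Mean 95% CI width, t-test v adjusted |
|---|---|---|---|---|
| 0 | 78.9% | 78.5% | 5.2% | 22.2 v 22.4 |
| 0.2 | 79.2% | 80.1% | 4.8% | not tabulated |
| 0.3 | 80.0% | 82.5% | 4.2% | 22.2 v 21.3 |
| 0.4 | 80.1% | 84.9% | 4.0% | not tabulated |
| 0.5 | 81.2% | 89.1% | 3.3% | 22.3 v 19.4 |
| 0.6 | 82.0% | 93.1% | 2.6% | 22.3 v 17.9 |

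The adjusted model's type I error stays between 4.7% and 5.2%. Permuted blocks of 4 within 2 or 4 strata (8,000 runs) lead to the same conclusion: t-test size is 4.4% to 4.7% at r = 0.3 and 2.7% to 3.3% at r = 0.5, and the Wilcoxon test behaves alike. Clipping the outcome to 0–100 does not change the picture.

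**4. If all 44 are analysed.** Power, t-test v adjusted: 87.0% v 86.7% (r = 0), 87.2% v 89.1% (0.3), 88.7% v 94.3% (0.5), 89.5% v 96.9% (0.6).

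**5. Where the loss sits.** At N = 36 the variance of the raw mean difference exceeds that of the adjusted estimate by a factor of only 1.03 at r = 0.3 and 1.12 at r = 0.5. The t-test's mean reported standard error exceeds the true sampling SD by factors of 1.03 and 1.09. Stratification has thus already given the point estimate much of the available gain, and a large part of the loss is an overstated standard error.

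**6. The imbalance rule.** Suppose a large difference means more than 0.5 SD (an assumption; the SAP gives no threshold). At N = 36 the baseline difference would exceed this in 1.4% of stratified trials, against 14.3% without stratification; at N = 44, in 0.6% against 10.5%.

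**7. Range restriction.** Eligibility requires past-year coverage below 80%. If uncapped coverage is roughly normal with mean 50–60 and SD 20–25 (assumed), an underlying r of 0.5 falls to 0.39–0.44 and 0.6 falls to 0.48–0.54.

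**The case against.** The strongest reply is that nothing here is invalid. The t-test matches the protocol's hypothesis and its sample-size method, the estimate is unbiased, and any error is on the safe side. This stands: the point concerns efficiency.

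The gain also rests wholly on an unknown r, and the documents give reasons for a modest one: the 80% cap, a 12-month baseline set against a 4-month outcome, and the protocol's own remark that use varies in summer and school holidays, which the past-year value includes. This stands too. At r = 0.2 the gain is under one point of power, and at 0.3 it is 2.5 points, so the rows for 0.5 and 0.6 are the favourable end. Against that, both measures are dispensing-based coverage in the same adolescents, and the investigators thought the factor important enough to stratify on.

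If nearly all 44 are analysed, t-test power is already about 87%. That is correct, but the interval would still be wider than necessary if r is moderate.

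The simulated outcome is normal with a linear baseline relation, whereas coverage is a bounded proportion. Clipping made no difference, but heavily skewed coverage was not examined. This is a reason to keep the rank test in the report.

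Finally, changing the primary test late carries its own risk of post hoc choice. The SAP is dated 12/15/2021 and section 2.2.2 gives a study end of 5/24/21. The fix has to allow for this.

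**Conclusion.** The point holds in its conditional form. The primary analysis omits the factor used to stratify, and the imbalance rule would rarely bring it in. If past-year coverage is prognostic, the planned test is conservative and its interval too wide. With 36 analysed, adjustment is worth about 2.5 points of power and 0.9 points of interval width at r = 0.3, rising to about 8 points of power (89.1 − 81.2 = 7.9) and 2.9 points of width (22.3 − 19.4) at r = 0.5. At r = 0 it costs 0.1 to 0.5 points of power. These figures assume median-split strata, a normal outcome and the protocol's difference and SD. Confidence in the size is only medium, because r is unknown and range restriction probably lowers it. This is a recommended improvement in efficiency; the planned test would not give a wrong answer.

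**What to change.** Make the primary analysis a linear model of the 4-month proportion of days covered on arm and the continuous past-year proportion of days covered, included whatever imbalance is observed. Report the adjusted mean difference with its 95% confidence interval. Keep the protocol's unadjusted t-test and the Wilcoxon test as named sensitivity analyses that are always reported. Replace the imbalance-triggered sentence in SAP 2.3.1 with this single fixed covariate.

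The amendment should state whether outcome data had been seen when it was made. If they had, keep the t-test as primary and report the adjusted model as a declared supportive analysis.

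The cost is a documented SAP amendment and one degree of freedom. No new data are needed.
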